9.3.3.2. Safety

Table 11 Primary Estimand for Secondary Safety Endpoint (Part A and Part B)

Primary Estimand	
Population	Male or female healthy participants aged 18 to 65 years
Variable/Endpoints	Incidence of all AEs, SAEs, and AESI through Day 29 ^a /Week 35
Treatment	100 mg/mL IM sotrovimab administered at dorsogluteal, anterolateral thigh, and deltoid injection sites and 62.5 mg/mL IM sotrovimab administered dorsogluteally
Strategy for Intercurrent Events or Events Leading to Missing Data	The intercurrent event of interest is participants receiving incomplete IM dose. The strategy of handling this intercurrent event will be a Treatment Policy Strategy, where all safety data after the intercurrent event will be included. Missing data will not be imputed.
Population-Level Summary	Frequency and Percentages of participants

^aDay 29 for anterolateral thigh and deltoid injection sites only as dorsogluteal injection sites are included in the primary safety endpoint.

Table 12 Primary Estimand for Secondary Safety Endpoint (Part C Cohort 1)

Primary Estimand	
Population	Male or female healthy participants aged 18 to 65 years
Variable/Endpoints	Incidence of all AEs, SAEs, and AESI through Week 35 (i.e., all events on the database at the time of DCO)
Treatment	Single IV infusion of sotrovimab at 3000 mg dose
Strategy for Intercurrent Events or Events Leading to Missing Data	The intercurrent event of interest is participants receiving incomplete IV dose. The strategy for handling this intercurrent event will be a Treatment Policy Strategy, where all safety data after the intercurrent event will be included. Missing data will not be imputed.
Population-Level Summary	Frequency and percentages of participants

For Part C optional Cohort 2, similar Estimand strategy will be followed for treatment: Single IV infusion of sotrovimab at up to 3000 mg dose.

9.3.4. Other Safety Endpoints

The estimand strategy for other safety endpoints, for all study parts, will be provided in the SAP.

9.3.5. Exploratory Endpoints

Further details of the analysis methods for the exploratory endpoints for all study parts will be provided in the SAP.

9.4. Interim Analysis

Part A and B:

In Part A and B, safety and tolerability data aggregated by treatment arm will be reviewed in-stream by the JSRT (see Section 10.1.5). A planned sentinel review will be conducted after approximately 5 participants per treatment arm complete at least Day 8 visit as described in Section 4.1.

Data from JSRT reviews may be used to inform study conduct or wider program decisions. These data will not be fully cleaned or undergo formal statistical analysis.

An IA will be conducted to review Part A data after approximately half of the participants in Part A complete at least Day 8 visit. The purpose of this interim is to inform the decision on whether to open Part B, and if needed the selection of treatment arms; further details of this IA will be specified in the SAP. Recruitment into Part A will continue with no pause at the time of the interim.

Thereafter, participants will continue to complete the remaining schedule of assessments as per the protocol.

Part C:

In Part C, aggregated safety and tolerability data will be reviewed in-stream by the JSRT (see Section 10.1.5). A planned in-stream review of safety lead-in data from Cohort 1 will be conducted after approximately 30 participants complete at least Day 8 visit as described in Section 4.1. The purpose of this review is to inform the decision to continue with Cohort 1 and whether to proceed with Cohort 2 including the selection of dose and infusion rate made by the JSRT and the clinical team. No dosing of further participants will take place until after the review is completed.

Data from JSRT reviews may be used to inform study conduct or wider program decisions. These data will not be fully cleaned or undergo formal statistical analysis.

An IA, including all data collected, will be conducted after approximately half of the participants in Cohort 1 complete at least Day 15, to support periodic data reviews across the program. Further details of this IA will be specified in the SAP.

Thereafter, participants will continue to complete the remaining schedule of assessments as per the protocol.

9.5. Sample Size Determination

Part A and B

The planned sample sizes for the number of evaluable participants in each treatment arm in Part A and Part B are based on precision estimation (using width of 90% CI) to assess the relative bioavailability. A sample size of approximately **50 evaluable participants** is selected for the 2 dorsogluteal arms in Part A (i.e., 500 mg IM of 62.5 mg/mL and 100 mg/mL sotrovimab arms, respectively) and approximately **25 evaluable participants** is selected for each of the 100 mg/mL sotrovimab thigh and deltoid arms in Part A and the 2 optional treatment arms in Part B. Therefore, the total number of evaluable participants planned in this study is **150 in Part A and 25 per treatment arm in Part B** (which may contain 1 or 2 treatment arms). To account for an expected 20% rate of non-evaluable participants approximately 190 participants will be randomized into Part A and 32 participants per/arm will be enrolled into Part B.

Sample size determinations are based on an assumed between participant coefficient of variation (CV_b) for AUC_{D1-29}, AUC_{inf}, and C_{max} of 50%.

For the primary PK objective, assuming a point estimate of 1 for the ratio of each **primary PK endpoints** (i.e., AUC_{D1-29} and C_{max}) between the treatment arms under the variability assumptions and the planned sample size of evaluable participants described above, the 90% CIs are predicted to be:

Parameters	Treatment Comparison	Sample Size	CV _b	90% CI
AUC _{D1-29} and C _{max}	100 mg/mL sotrovimab dorsogluteal arm vs 62.5 mg/mL sotrovimab dorsogluteal arm	50 per arm	50%	(0.85, 1.17)

Similarly, for the secondary PK objective, assuming a point estimate of 1 for the ratio of each **secondary PK endpoints** (i.e., AUC_{D1-29}, AUC_{inf}, and C_{max}) between the treatment arms under the variability assumptions and the planned sample size of evaluable participants described above, the 90% CIs are predicted to be:

Parameters	Treatment Comparisons	Sample Size	CV _b	90% CI
AUC _{D1-29} and C _{max}	100 mg/mL sotrovimab anterolateral thigh or deltoid arm vs 62.5 mg/mL sotrovimab dorsogluteal arm	25 vs 50	50%	(0.80, 1.25)
AUC _{inf}	100 mg/mL sotrovimab dorsogluteal arm vs 62.5 mg/mL sotrovimab dorsogluteal arm	50 per arm	50%	(0.85, 1.17)
AUC _{inf}	100 mg/mL sotrovimab anterolateral thigh or deltoid arm vs 62.5 mg/mL sotrovimab dorsogluteal arm	25 vs 50	50%	(0.80, 1.25)

Part C

The planned sample size for the number of evaluable participants in Part C Cohort 1 is 200. With 200 participants (intend to target up to approximately 20 Japanese participants), there is a 90% chance of observing at least 1 AE of interest, if the true incidence rate of that AE is not below 1.14%. Of note, in COMET-ICE, the IRR rate was 1.14%. The sample size has been selected to provide sufficient safety and tolerability data to evaluate the higher IV dose of sotrovimab proposed for this part.

Part C Cohort 2 will be considered optional and will be opened following safety lead-in review based on Part C Cohort 1 data. The planned sample size for the number of evaluable participants in Part C Cohort 2 is 50. With 50 participants, there is a 90%

chance of observing at least 1 AE of interest, if the true incidence rate of that AE is not below 4.5%. Cohort 2 will supplement the data from Cohort 1 and may be combined at the end of study if the same dose is administered in both cohorts.

The precision of event rate estimation is shown in the table below, as indicated by the width of 95% CIs. More specifically, the total number of 250 participants reflects the precisions when summarizing over both the cohorts at the end of study if the same dose is administered.

Precision of Estimated Event Rate:

Total Number of Participants	Observed Event Rate	Number of Participants with a Particular Event Observed	95% CI
200 (individual study size for Part C Cohort 1)	0.5%	1	(0.01%, 2.75%)
	1.0%	2	(0.12%, 3.57%)
	2.0%	4	(0.55%, 5.04%)
	5.0%	10	(2.42%, 9.00%)
	10.0%	20	(6.22%, 15.02%)
	50.0%	100	(42.87%, 57.13%)
50 (individual study size for Part C Optional Cohort 2)	0.5%	1	(0.05%, 10.65 %)
	1.0%	1	(0.05%, 10.65%)
	2.0%	1	(0.05%, 10.65%)
	5.0%	3	(1.25%, 16.55%)
	10.0%	5	(3.33%, 21.81%)
	50.0%	25	(35.53%, 64.47%)

Total Number of Participants	Observed Event Rate	Number of Participants with a Particular Event Observed	95% CI
250 (combined study size for Part C Cohort 1 and Optional Cohort 2 if dose is the same)	0.5%	2	(0.10%, 2.86%)
	1.0%	3	(0.25%, 3.47%)
	2.0%	5	(0.65%, 4.61%)
	5.0%	13	(2.80%, 8.73%)
	10.0%	25	(6.58%, 14.41%)
	50.0%	125	(43.63%, 56.37%)

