9. STATISTICAL CONSIDERATIONS

9.1. Statistical Hypotheses

Part A:

The primary objectives are to estimate the relative bioavailability, safety, and tolerability of single-dose high-concentration sotrovimab administered intramuscularly in healthy participants. There are no formal statistical hypotheses planned.

Part B:

The secondary objectives are to estimate the relative bioavailability, safety, and tolerability of single-dose high-concentration sotrovimab administered intramuscularly in healthy participants. There are no formal statistical hypotheses planned.

Part C:

The primary objectives are to characterize the safety and tolerability of IV sotrovimab administered in healthy participants. There are no formal statistical hypotheses planned.

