6.2.2. Pharmacokinetic Parameters

For the purposes of calculating summary statistics and for statistical analysis, all PK parameters with the exception of T_{max} , T_{last} , $t_{1/2}$ and λ_z will be \log_e transformed.

Between subject coefficient of variation %CV_b will be calculated according to the following methods:

Untransformed Data : $\frac{SD}{mean} \times 100$,

Transformed Data : $\sqrt{e^{SD^2} - 1} \times 100$,

where SD^2 = variance of \log_e transformed data.

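### The predicted 90% CI of (0.80, 1.25) for the 25-versus-50 PK comparisons does not follow from the stated inputs, which give about (0.82, 1.21)

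*Protocol*

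**What the plan says.** Protocol 9.5 states that the evaluable numbers per arm in Parts A and B are "based on precision estimation (using width of 90% CI) to assess the relative bioavailability". Protocol 9.1 adds: "There are no formal statistical hypotheses planned". There is therefore no power calculation behind the arm sizes.

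The inputs are set out in the same section: "A sample size of approximately 50 evaluable participants is selected for the 2 dorsogluteal arms in Part A", with about 25 in each of the thigh and deltoid arms. On variability: "Sample size determinations are based on an assumed between participant coefficient of variation (CV_b) for AUC_{D1-29}, AUC_{inf}, and C_{max} of 50" per cent. The secondary table is introduced by "assuming a point estimate of 1 for the ratio of each secondary PK endpoints" and then, "under the variability assumptions and the planned sample size of evaluable participants described above, the 90% CIs are predicted to be", the intervals follow.

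The row labelled "100 mg/mL sotrovimab anterolateral thigh or deltoid arm vs 62.5 mg/mL sotrovimab dorsogluteal arm" appears twice, for AUC_D1-29 and Cmax together and for AUCinf. Each time it shows 25 vs 50, CV 50% and (0.80, 1.25). The rows comparing the two dorsogluteal arms show 50 per arm, CV 50% and (0.85, 1.17). SAP 5 repeats all of these rows with the same numbers.

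**The concern.** Doubling the reference arm from 25 to 50 should narrow the interval visibly compared with 25 per arm. Yet the 25-vs-50 rows carry the interval that one would expect for two arms of 25.

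Predicted CI width is the only quantitative argument offered for the 25-participant arms. If the figure is wrong, the documents do not describe the precision that the chosen design delivers, and a reader who judges whether 25 is enough, or more than enough, is working from the wrong number.

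**Working it through.** **Inputs.** Evaluable n of 25 and 50, CV 50%, assumed ratio 1 and 90% confidence, all from Protocol 9.5 and SAP 5. The 20% non-evaluable allowance plays no part, because the intervals are stated for evaluable participants. SAP 6.2.2 gives the CV of log-transformed data as sqrt(exp(SD²) − 1), "where SD^2 = variance of \log_e transformed data". Inverting it:

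σ = sqrt(ln(1 + 0.5²)) = sqrt(ln 1.25) = 0.4724

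**Formula.** With a ratio of 1, the 90% CI is exp(± q × σ × sqrt(1/n1 + 1/n2)), where q is the 95th percentile of t on n1 + n2 − 2 degrees of freedom.

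**Reproducing the plan's own 50-per-arm row.** SE = 0.4724 × sqrt(1/50 + 1/50) = 0.0945. With t on 98 df the interval is (0.8548, 1.1699), which rounds to the printed (0.85, 1.17). The normal quantile gives 0.8561 and a pooled 144 df gives 0.8552 for the lower limit. Both round to 0.86, so the two-sample t is the version that matches.

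**The row as labelled, 25 vs 50.** SE = 0.4724 × sqrt(1/25 + 1/50) = 0.1157.

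| Variant | 90% CI, 25 vs 50 |
|---|---|
| t, 73 df | (0.8247, 1.2126) |
| normal quantile | (0.8267, 1.2096) |
| four-arm ANCOVA, 144 df | (0.8257, 1.2111) |
| t, 24 df (smaller arm only) | (0.8204, 1.2189) |
| log-SD taken as 0.50, t on 73 df | (0.8154, 1.2263) |
| 95% assurance on the SD | (0.8036, 1.2444) |

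A 95% CI in place of 90% gives (0.7941, 1.2594). None of these rounds to (0.80, 1.25).

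**25 vs 25.** SE = 0.4724 × sqrt(1/25 + 1/25) = 0.1336. With t on 48 df the interval is (0.7992, 1.2512). The normal quantile gives (0.8027, 1.2458). Both round to (0.80, 1.25).

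**A check that does not need the CV.** With one common SD, going from 50 vs 50 to 25 vs 50 multiplies the log half-width by sqrt(0.06)/sqrt(0.04) = sqrt(1.5) = 1.22, apart from a negligible change in the t quantile. The printed upper limits imply ln 1.25 / ln 1.17 = 0.223 / 0.157 = 1.42, close to sqrt(2) = 1.41, the factor for 25 vs 25. Rounding does not close the gap: the smallest ratio the printed upper limits allow is ln 1.245 / ln 1.175 = 0.219 / 0.161 = 1.36.

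**What would give (0.80, 1.25).** At 25 vs 50 the CV would have to be about 59% (58% to 60% allowing for rounding of the upper limit). At 59%, the 50-per-arm row would read about (0.83, 1.20), not (0.85, 1.17). Alternatively, at CV 50%, about 17 evaluable participants against 50 would do: t on 65 df gives (0.8015, 1.2477).

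**Size.** Stated log half-width ln 1.25 = 0.223; computed ln 1.2126 = 0.193; ratio 0.223 / 0.193 = 1.16.

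**The case against.** The arithmetic is not in dispute. The case on the other side concerns weight and wording.

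- **Direction and consequence.** The design is more precise than promised. The affected rows are secondary, the primary row is correct, no acceptance limit is set for the ratio and no test depends on the figure. This stands, and it limits the urgency. It does not make the printed interval right, and in a plan sized on precision alone the precision figure is what the reader relies on.
- **Cause.** The documents do not show how (0.80, 1.25) was obtained. A 25-vs-25 calculation is an inference, supported by a match to two decimals at the stated CV. Other inputs, such as 17 vs 50 or a CV near 59%, would also give it, but they contradict the row's own label or the 50-per-arm row.
- **Choice of quantile.** The lower limit rounds to 0.82 with the two-sample t and to 0.83 with the normal quantile or the 144 df of the planned ANCOVA. That is fair, so the correction should name its method. The two-sample t is the one that agrees with the rows already correct.
- **Part B.** No predicted interval is printed for Part B, and SAP 1 leaves Part B to a later amendment, so no Part B figure is wrong. Protocol 9.5 does plan 25 evaluable participants per Part B arm, and Protocol 9.3.1 compares them with the same Part A reference arm, so a reader would naturally borrow this row.
- **Cost.** Reissuing a protocol takes more than editing a table, given the approval steps in Protocol 10.1.1. That affects timing, not substance.

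**Conclusion.** The concern holds. At the stated CV of 50%, ratio of 1 and 25 vs 50 evaluable participants, the predicted 90% CI is about (0.82, 1.21), not (0.80, 1.25). The printed log half-width is about 16% too wide. The same error stands in two rows of Protocol 9.5 and two rows of SAP 5.

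The conclusion assumes a common log-scale SD of 0.4724 in both arms, derived from the SAP's own CV formula, and the two-sample t quantile. Changing the quantile moves the lower limit only between 0.82 and 0.83. The internal inconsistency between the 50-per-arm and 25-vs-50 rows holds at any single CV. It is a reporting error in the conservative direction: it should be corrected, but it does not threaten the trial's conclusions.

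**What to change.** In both 25-vs-50 rows of Protocol 9.5 and of SAP 5, replace (0.80, 1.25) with (0.82, 1.21). Add a short note that the predicted intervals use a two-sample t quantile on n1 + n2 − 2 degrees of freedom with SD = sqrt(ln(1 + CV²)). If the sponsor intended a different assumption for these rows, state it instead and recompute the 50-per-arm rows under the same assumption.

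The cost is two table cells and a note in each document. Enrolment, analysis methods and the primary comparison are unchanged. The SAP can be corrected at its next version, and the protocol correction can wait for the next amendment made for another reason.

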10. SUPPORTING DOCUMENTATION AND OPERATIONAL CONSIDERATIONS

10.1. Appendix 1: Regulatory, Ethical, and Study Oversight Considerations

10.1.1. Regulatory and Ethical Considerations

- This study will be conducted in accordance with the protocol and with:
 - Consensus ethical principles derived from international guidelines including the Declaration of Helsinki and CIOMS international ethical guidelines
 - Applicable ICH GCP guidelines
 - Applicable laws and regulations
- The protocol, protocol amendments, ICF, IB, and other relevant documents (e.g., advertisements) must be submitted to an IRB/IEC by the investigator and reviewed and approved by the IRB/IEC before the study is initiated.
- Any amendments to the protocol will require IEC/IRB approval before implementation of changes made to the study design, except for changes necessary to eliminate an immediate hazard to study participants.
- Protocols and any substantial amendments to the protocol will require health authority approval prior to initiation except for changes necessary to eliminate an immediate hazard to study participants.
- The investigator will be responsible for the following:
 - Providing written summaries of the status of the study to the IRB/IEC annually or more frequently in accordance with the requirements, policies, and procedures established by the IRB/EC
 - Notifying the IRB/IEC of SAE or other significant safety findings as required by IRB/IEC procedures
 - Providing oversight of the conduct of the study at the site and adherence to requirements of 21 CFR, ICH guidelines, the IRB/IEC, European regulation 536/2014 for clinical studies (if applicable), European Medical Device Regulation 2017/745 for clinical device research (if applicable), and all other applicable local regulations

10.1.2. Financial Disclosure

Investigators and sub-investigators will provide the sponsor/designee with sufficient, accurate financial information as requested to allow the sponsor/designee to submit complete and accurate financial certification or disclosure statements to the appropriate regulatory authorities. Investigators are responsible for providing information on

financial interests during the course of the study and for 1 year after completion of the study.

10.1.3. Informed Consent Process

- The investigator or his/her representative will explain the nature of the study, including the risk and benefits, to the participant and answer all questions regarding the study.
- Participants must be informed that their participation is voluntary. Participants will be required to sign a statement of informed consent that meets the requirements of 21 CFR 50, local regulations, ICH guidelines, privacy and data protect requirements, where applicable, and the IRB/IEC or study center.
- The medical record must include a statement that written informed consent was obtained before the participant was enrolled in the study and the date the written consent was obtained. The authorized person obtaining the informed consent must also sign the ICF.
- Participants must be re-consented to the most current version of the ICF(s) during their participation in the study.
- A copy of the ICF(s) must be provided to the participant.
- If follow-up information from a treating physician or other licensed medical practitioner is required for a medical device incident with an AE/SAE involving an associated person(s), the Associated Person Safety Reporting Information and Authorization Letter must be signed by the associated person to obtain consent.
- Participants who are rescreened are required to sign a new ICF.

GSK (alone or working with others) may use participant's coded study data and samples and other information to carry out this study; understand the results of this study; learn more about sotrovimab or about the study disease; publish the results of these research efforts; work with government agencies or insurers to have sotrovimab approved for medical use or approved for payment coverage.

10.1.4. Data Protection

- Participants will be assigned a unique identifier by the sponsor/designee. Any participant records or datasets that are transferred to the sponsor/designee will contain the identifier only; participant names or any information which would make the participant identifiable will not be transferred.
- The participant must be informed that his/her personal study-related data will be used by the sponsor/designee in accordance with local data protection law. The level of disclosure must also be explained to the participant who will be required to give consent for their data to be used as described in the informed consent.
- The participant must be informed that his/her medical records may be examined by Clinical Quality Assurance auditors or other authorized personnel appointed by the sponsor/designee, by appropriate IRB/IEC members, and by inspectors from regulatory authorities.

10.1.5. Committees Structure

10.1.5.1. Joint Safety Review Team

A JSRT comprised of team members from clinical research, global safety, and statistics from GSK and Vir, will review safety data throughout the study from all participants. The responsibilities of the JSRT and frequency of assessments will be outlined in the JSRT charter. The JSRT will review safety data from a sentinel cohort for each study Part and will review Part A data to inform Part B decisions, as described in Section 4.1.

Additionally, the JSRT will review safety lead-in data from Part C Cohort 1 to decide to continue with Cohort 1 and whether to proceed with Cohort 2 (with a selection of different dose and infusion rate than Cohort 1). JSRT may request additional data before making a decision.

10.1.6. Dissemination of Clinical Study Data

- Where required by applicable regulatory requirements, an investigator signatory will be identified for the approval of the CSR. The investigator will be provided reasonable access to statistical tables, figures, and relevant reports and will have the opportunity to review the complete study results at a GSK site or other mutually agreeable location.
- The sponsor or designee will also provide all investigators who participated in the study with a summary of the study results and will tell the investigators what treatment their patients' received. The investigator(s) is/are encouraged to share the summary results with the study participants, as appropriate.
- Under the framework of the SHARE initiative, GSK intends to make anonymized participant-level data from this study available to external researchers for scientific analyses or to conduct further research that can help advance medical science or improve patient care. This helps ensure the data provided by study participants are used to maximum effect in the creation of knowledge and understanding. Requests for access may be made through www.clinicalstudydatarequest.com.
- The procedures and timing for public disclosure of the protocol and results summary and for development of a manuscript for publication for this study will be in accordance with the sponsor/GSK Policy.
- The sponsor/GSK intends to make anonymized patient-level data from this study available to external researchers for scientific analyses or to conduct further research that can help advance medical science or improve patient care. This helps ensure the data provided by study participants are used to maximum effect in the creation of knowledge and understanding.

